4.2.1.2 Risks

Although this study presents minimal risks to the participant, there is the potential for some risk when any medical procedure is performed.

Anticipated Device Effects

These are known effects of the CoolSculpting procedure, previously recorded in prior studies as transient and/or temporary effects related to the cold application and/or vacuum pressure inherent in the treatment. Anticipated effects of the device which will not be considered AEs include:

- inflammation of the subcutaneous fat layer, which is a desired effect of the procedure;
- sensations of coldness, stinging, burning, pinching, or pressure associated with placement of the applicator and the initiation of the cold treatment;
- known skin effects (eg, blanching; erythema, bruising, purpura, petechiae, swelling, discomfort, tenderness, or soreness at the treatment site, all mild to moderate in nature), which are temporary effects that resolve spontaneously shortly after the procedure; and
- localized sensory changes (eg, numbness, tingling) at the treatment area spontaneously resolving **without medical intervention within 12 weeks** of the procedure.

If the severity of these anticipated effects causes disruption to the participant's daily activities, then they will be evaluated as a potential adverse effect.

Potential Adverse Effects

Potential Adverse Effect	Description
Severe Bruising	The appearance of bruising (purple discoloration); purpura (purple colored spots or patches); or petechiae (pin point red dots) that is rated as severe by the investigator.
Prolonged Bruising	Bruising lasting longer than 1 month.
Severe Erythema	The appearance of erythema (redness) that is rated as severe by the investigator.
Prolonged Erythema	Erythema lasting longer than 2 weeks.
Severe Swelling	The appearance of swelling (edema) that is rated as severe by the investigator.
Prolonged Swelling	Swelling lasting longer than 1 month.
First Degree Burn	Skin damage from burns may be due to hot or cold. A first degree burn is superficial and causes local inflammation of the skin. The inflammation is characterized by pain, redness, and mild swelling. The skin may be very tender to touch.
Second Degree Burn	Second degree burns are deeper and, in addition to the pain, redness, and inflammation, there is also blistering of the skin.

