An ADE is defined in accordance with ISO 14155 as “an adverse event related to the use of an investigational medical device.” This definition includes any AEs resulting from insufficient or inadequate instructions for use, deployment, implantation, installation, or operation, or any malfunction of the investigational medical device as well as any event resulting from use error (per ISO 62366) or from intentional misuse of the investigational medical device.

Device Deficiency or Complaints

A device deficiency is defined in accordance with ISO 14155 as inadequacy of a medical device including issues with respect to its identity, quality, durability, reliability, safety, or performance. Device deficiencies include malfunctions, use errors, and inadequate labelling.

If a device deficiency occurs, the investigator will notify Allergan using the CRF. Device deficiencies shall be documented throughout the study and appropriately managed by Allergan. The Clinical Trial Site will enter all the information regarding device deficiency into the appropriate CRFs. Device deficiencies associated with AEs will also require completion of SAE forms. Allergan shall review all device deficiencies and determine and document in writing whether they could have led to a SADE. These shall be reported to the regulatory authorities and IRBs as required by Federal regulations.

Assessment of Severity

Severity is a clinical determination of the intensity of an AE. The severity assessment for a clinical AE will be assigned a category by the investigator as follows:

Mild	An AE that is easily tolerated by the participant, causes minimal discomfort, may require only minimal treatment and does not interfere with everyday activities.
Moderate	An AE that is sufficiently discomforting to interfere with normal everyday activities; intervention may be needed, but poses no significant or permanent risk of harm.
Severe	An AE that prevents normal everyday activities; treatment or other intervention usually needed.

If there is a change in severity of an AE, it must be recorded as a separate event.

Assessment of Causality

Relationship to a device refers to a determination of the relationship (if any) between an AE and the device. A causal relationship is present if the investigator determines that there is a reasonable possibility that the AE may have been caused by the device.

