6.1. General Methods

- [REDACTED] will be used to produce all listings, summaries, and analyses described in this document.
- Unless otherwise specified, summaries will be presented for each treatment area and overall.
- Continuous variables will be summarized using the number of participants with observed values (n), mean, standard deviation (SD), median, 1st and 3rd quartiles (Q1, Q3), minimum (min), and maximum (max). Categorical variables will be summarized using number of observations (n), frequency and percentages of participants.
- All relevant participant data will be included in listings. All participants entered into the database will be included in participant data listings.
- Unscheduled assessments for visit based parameters will be listed but not summarized or analyzed; only data recorded on the nominal study visits will be included in summaries and analyses.
- Medical history data will be listed for the Enrolled Population sorting by participant number, start date (placing missing and partial dates first) and end date, then alphabetically by System Organ Class (SOC) and Preferred Term (PT) within SOC.
- Prior and concomitant medications will be listed for the Enrolled Population, sorted by participant number, start date (placing missing and partial dates first) and end date, alphabetically by Anatomic Therapeutic Chemical (ATC) level 2 category and then by preferred name within ATC level 2 category.
- All AEs will be listed, sorting by participant number, start date (placing missing and partial dates first) and end date, alphabetically by SOC, and then by PT within SOC. AE duration in days will be calculated as (end date - start date + 1) and included in the data listings.

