9.2. Adverse Events

An AE is any untoward medical occurrence, unintended disease or injury, or untoward clinical signs (including abnormal laboratory findings) in participants, users or other persons, whether or not related to the investigational medical device or the comparator device. This definition includes events related to the procedures involved.

An SAE is defined as an AE that:

- led to death
- led to serious deterioration in the health of the participant, that either resulted in
 - a life-threatening illness or injury; or
 - a permanent impairment of a body structure or a body function, or
 - in-patient or prolonged hospitalization; or
 - medical or surgical intervention to prevent life-threatening illness or injury or permanent impairment to a body structure or a body function; or
 - if a participant becomes pregnant, then spontaneous abortion, fetal distress, fetal death, or a congenital abnormality or birth defect is considered an SAE

AEs will be coded using MedDRA V22.1 or higher.

AEs will be defined as treatment-emergent if they start after the first treatment. AEs with missing or partial dates will be handled according to Section **Error! Reference source not found.** with respect to assigning treatment-emergence. As a conservative approach, AEs are considered treatment-emergent unless there is clear indication that the event occurred before the first treatment in the study. In general, only TEAEs will be included in the summary tables, but all AEs will be included in the listings.

The number of participants and the number of TEAEs will be tabulated by SOC and PT, sorted by the decreasing overall frequency of SOC and then by PT in decreasing frequency within each SOC. For summaries by SOC, PT, and maximum severity, a participant will be counted once at the highest severity level for which the event occurred at the SOC level and the highest severity level for each unique PT within that SOC level. Therefore, participants will only contribute once to each PT and once to each SOC level. Severity will be assessed as mild, moderate, or severe. For summaries by SOC, PT, and maximum

This document is confidential.

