relationship (to study device or to study procedure), a participant will be counted once at the highest causality level for which the event occurred at the SOC level, and the highest causality level for each unique PT within that SOC level. Therefore, participants will only contribute once to each PT and once to each SOC level. Causality will be assessed in relation to the study device and the study procedure as not related, unlikely, possible, probable, or causal relationship.

An TEAE will be defined as device-related or procedure-related if it is assessed as unlikely, possible, probable, or causal relationship.

The following tables will be produced:

- An overall summary of the number and percentage of participants reporting TEAEs, device-related TEAEs, procedure-related TEAEs, and SAEs, including the total number of device-related TEAEs, procedure-related TEAEs, and TESAEs by overall.
- TEAEs, overall and by SOC and PT.
- TEAEs by maximum severity, overall and by SOC and PT.
- TESAEs, overall and by SOC and PT.

Listings of all AEs, SAEs, and AEs leading to discontinuation by participant will be presented.

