9.3. Adverse Device Event

An ADE is any AE related to the use of an investigational medical device, including those events resulting from insufficient or inadequate instructions for use, deployment, implantation, installation, or operation, or any malfunction of the investigational medical device. This definition includes any event resulting from use error or from intentional misuse of the investigational medical device.

A serious adverse device event (SADE) is an ADE that resulted in any of the consequences characteristic of an SAE (all device or surgical related).

The number of participants and the number of ADEs will be tabulated by SOC and PT, sorted by decreasing overall frequency of SOC and then by PT within SOC.

The following tables will be produced:

- ADEs, overall and by SOC and PT.
- SADEs , overall and by SOC and PT.
- ADEs with maximum severity , overall and by SOC and PT.

All ADEs will be listed, sorting by participant number, start date (placing missing and partial dates first) and end date, alphabetically by SOC, and then by PT within SOC. ADE duration in days will be calculated as (end date - start date + 1) and included in the data listings.

This document is confidential.

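### One continuous adverse event can be counted several times in the event totals, because each severity change becomes a new record and the SAP has no visible rule linking such records

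*Protocol*

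**What the plan says.** Under the heading on assessment of severity, Protocol section 8.2.1 states: "If there is a change in severity of an AE, it must be recorded as a separate event". The rule makes no distinction between worsening and improvement.

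The SAP then counts events as well as participants. Section 9.2: "The number of participants and the number of TEAEs will be tabulated by SOC and PT". The overall summary in the same section gives participant numbers, "including the total number of device-related TEAEs, procedure-related TEAEs, and TESAEs by overall". Section 9.3: "The number of participants and the number of ADEs will be tabulated by SOC and PT". Section 10 repeats the overall summary and the SOC/PT table by site and by generation.

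Duration is defined from the dates of the event. SAP section 6.1: "AE duration in days will be calculated as (end date - start date + 1) and included in the data listings". Section 9.3 repeats this for ADEs: "ADE duration in days will be calculated as (end date - start date + 1) and included in the data listings".

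Protocol section 4.2.1.2 defines some potential adverse effects by how long the effect lasts. Prolonged erythema is "Erythema lasting longer than 2 weeks" and prolonged bruising is "Bruising lasting longer than 1 month". The limit is also 1 month for swelling, and 12 weeks for sensory changes.

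Neither document shows a rule for joining successive severity records of one event. SAP section 12, which lists changes from the protocol, does not mention the matter.

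**The concern.** The protocol's recording unit is a period at one severity level. A reader of a safety table will take the unit to be an event. Where the two differ, the plan's own rules yield a wrong event total, not merely an underspecified one.

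The totals by site are the most exposed. A site that records each step of fading will show more events than a site that does not, for the same clinical course.

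The listings have a related weakness. If an event is split, no line need show its full length, although that length is what the protocol uses to call an effect prolonged. The study is intended to support a regulatory submission (Protocol section 4.2), so event totals and listings should be readable at face value.

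**Working it through.** The plan gives no figure to reproduce here. The check follows one event through the stated rules.

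**Inputs**
- Recording rule: Protocol 8.2.1, one new record per severity change.
- Event counts: SAP 9.2, 9.3 and 10.
- Duration: end − start + 1 (SAP 6.1 and 9.3).
- Limits T from Protocol 4.2.1.2: erythema 14 days; bruising and swelling 1 month, taken as 30 days; sensory change 12 × 7 = 84 days.
- Assumption: a new record starts the day after the previous severity level ends. The documents do not state this.

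**Counts.** With k severity changes, one event gives k + 1 records.

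| Changes k | Records counted as events | Participants counted |
|---|---|---|
| 0 | 1 | 1 |
| 1 | 2 | 1 |
| 2 | 3 | 1 |

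**Durations.** Take a continuous event of D days with one change after day s. The first record covers days 1 to s, and its duration is s − 1 + 1 = s. The second covers days s + 1 to D, and its duration is D − (s + 1) + 1 = D − s.

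Both records are at or below T only if D − T ≤ s ≤ T. This requires D ≤ 2T. For T < D ≤ 2T, the number of such change days is 2T − D + 1, out of D − 1 possible days.

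| Effect | T | D | Change days for which neither record exceeds T |
|---|---|---|---|
| Erythema | 14 | 15 | 1 to 14 (14 of 14) |
| Erythema | 14 | 20 | 6 to 14 (9 of 19) |
| Erythema | 14 | 28 | 14 only (1 of 27) |
| Erythema | 14 | 29 or more | none |
| Bruising, swelling | 30 | 45 | 15 to 30 (16 of 44) |
| Bruising, swelling | 30 | 61 or more | none |
| Sensory | 84 | 100 | 16 to 84 (69 of 99) |
| Sensory | 84 | 132 | 48 to 84 (37 of 131) |
| Sensory | 84 | 169 or more | none |

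These are counts of possible change days, not probabilities. Taking a month as 28 to 31 days moves the upper bound 2T for bruising and swelling from 56 to 62 days.

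**Two examples**
- Erythema severe for 10 days, then mild for 8: 10 + 8 = 18 > 14, but the listing shows 10 and 8. It is counted as two events.
- Numbness of 132 days with a change after day 30: records of 30 and 132 − 30 = 102 days. Since 102 > 84, the listing still shows a prolonged record. It is also counted as two events.

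**If the assumption fails.** If the new record repeats the original onset date, the last record shows the full D days. The event is still counted k + 1 times.

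**The case against.** There is a good case that this is small.

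- The planned safety summary is the number and proportion of participants with events (Protocol 9.3.3; SAP section 9). A participant with three records of one preferred term still counts once, and SAP 9.2 says so for the maximum-severity and maximum-relationship tables. This stands. A reader might infer that the adverse event rates are inflated; the participant-based rates are not.
- Protocol 4.2.1.2 does not treat most fading treatment-site effects as AEs. Mild to moderate skin effects that resolve shortly, and sensory changes that resolve within 12 weeks, are anticipated effects unless they disrupt daily activities. This also stands and limits how often splitting occurs. It does not cover severe effects, disruptive effects, or listed events such as burns and induration.
- A reader might infer that prolonged events will drop out of the results. The documents do not support that. Calculated duration appears only in listings and classifies nothing in the SAP. A non-severe bruise that does not disrupt activities becomes an AE because the whole bruise outlasted a month, which is judged before any SAP formula applies. Listings are sorted by participant and start date, so the component records stay visible.
- The dating of a severity-change record is unclear. Protocol 8.2.1 asks when the event first occurred and when it resolved, says earlier AEs are updated, and lists duration among the CRF items. This makes shortened durations possible rather than certain, but leaves the double count in place.
- The background studies give no frequency of severity change. The long events that they report with a grade (mild erythema of 15 days, mild numbness of 132 days) are described at one grade. They show that lengths beyond the limits occur, not that such events split.
- The CRF is not available, and SAP section 19 places the table and listing shells in a separate document. A linking rule could be there, so its absence is established only for the text at hand.

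**Conclusion.** The event-count problem holds on the stated rules alone: a continuous AE with k severity changes adds k + 1 to the numbers of TEAEs and, where related, to the ADE and related-event totals. This includes the totals by site and by generation. How far the study totals would rise cannot be estimated, because the documents give no rate of severity change.

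The duration problem is conditional. With one change, it hides a breach of a limit only if the episode is no longer than twice the limit, the change falls in the right interval, and the new record is dated from the change. Its effect is confined to listings.

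No participant-level count or proportion changes, and extra events overstate harm rather than conceal it. The conclusion assumes that no linking rule exists in the CRF or the shells. The correction is worth making because the totals are planned outputs and the cost is low.

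**What to change.** Keep the severity-change records, since the protocol requires them, and link them with an episode identifier specific to the participant, the event term and the treatment site.

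- SAP 9.2, 9.3 and 10: count each linked episode once in the event totals, at its maximum severity and maximum relationship.
- SAP 6.1 and 9.3: list the episode duration, from first onset to final resolution, beside the record-level dates.

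Two simpler options have drawbacks. Linking only by preferred term and adjoining dates could merge separate events, since a participant may have both arms and both thighs treated. Recording one AE at its maximum severity would lose the severity history.

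The cost is one CRF or derivation field, a few sentences in the SAP and slightly more programming. No extra visits or participants are needed.

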8.2.1.1 Serious Adverse Events

Serious Adverse Event Definition

An SAE is defined as an AE that:

- led to death
- led to serious deterioration in the health of the participant, that either resulted in
 - a life-threatening illness or injury; or
 - a permanent impairment of a body structure or a body function, or
 - in-patient or prolonged hospitalization; or
 - medical or surgical intervention to prevent life-threatening illness or injury or permanent impairment to a body structure or a body function; or
 - if a participant becomes pregnant, then spontaneous abortion, fetal distress, fetal death, or a congenital abnormality or birth defect is considered an SAE

In addition, medical and scientific judgment is required to decide if prompt notification is required in situations other than those defined for SAEs above. This may include any event that the investigator regards as serious that did not strictly meet the criteria above but may have jeopardized the participant or required intervention to prevent one of the outcomes listed above, or that would suggest any significant hazard, contraindication, side effect, or precaution that may be associated with the use of the investigational product.

Serious Adverse Device Effect (SADE)

All device or surgical related SAEs must be entered into the EDC system within 24 hours of being notified of the event. The sponsor will be notified by EDC system once the SAE electronic form has been submitted.

- The relationship of the clinical event to the devices and procedure should be reported on the Form and will be determined by the investigator.
- Following evaluation of each SAE, the responsible ethics committee will be notified as appropriate based on national regulations.
- All SAEs that occur from the time the ICF is signed through to their final study visit must be reported to the sponsor. In addition to entering the information into the EDC system, the investigator must:
- Notify the sponsor immediately (within 24 hours) by emailing the Allegan Product Surveillance team at: [contact]

The following SAE information should be provided:

- Description of the symptom event (including treatment dates, areas treated, event description, etc)
- Applicator(s) and Serial Number used during treatment
- Classification of ‘serious’ or ‘not serious’
- Severity
- Date of first occurrence and date of resolution (if applicable)
- Action taken
- Causal relationship
- Outcome of event: report as much information within 24 hours regardless of the amount of information available, although the investigator is expected to provide as much information as possible.

Obtain and maintain in his/her files all pertinent medical records, information, and medical judgments from colleagues who assisted in the treatment and follow-up of the participant.

Provide the sponsor with a complete, written case history (AE report form) that includes a statement as to whether the event was or was not related to the use of the investigational device or procedure.

The sponsor (or its representative) will report all SAEs associated with the use of the study device to the regulatory agencies (Ethics Committee, Competent Authorities) as appropriate according to relevant standard operating procedures and to the national laws of the country where the trial is performed.

In every SAE, appropriate measures should be taken to treat/resolve and monitor the participant. The investigator should keep Allergan closely informed of the progress as related to the SAE. Any participants who are withdrawn from the study due to an AE shall still be followed until the outcome is resolved.

Details of the procedures to be followed if a pregnancy occurs are provided in Section [6.3.4](#).

8.2.1.2 Unanticipated Serious Adverse Device Effect

Unanticipated Serious Adverse Device Effect Definition

An unanticipated serious ADE is a SADE effect that by its nature, incidence, severity, or outcome has not been identified in the current version of the risk analysis report.

8.2.2 Warnings and Precautions

Unauthorized modification or repair of the control unit, its components, or supplies may result in unsafe conditions and/or impaired performance. No modification of this equipment is allowed without express authorization from Allergan. Any unauthorized modification or repair will void the warranty.

CoolSculpting System use has not been studied in children, those who are pregnant or lactating, or who have:

- Known sensitivity to cold such as cold urticaria, Raynaud's disease, or Chilblains (pernio)
- Known sensitivity or allergy to fructose, glycerin, isopropyl alcohol, or propylene glycol
- Impaired peripheral circulation in the area to be treated
- Neuropathic disorders such as post-herpetic neuralgia or diabetic neuropathy
- Impaired skin sensation
- Open or infected wounds
- Bleeding disorders or concomitant use of blood thinners
- Recent surgery or scar tissue in the area to be treated
- Hernia in or adjacent to the treatment site
- Skin conditions such as eczema, dermatitis, or rashes in the area to be treated

